Subject Description:	Eligible subjects include those \geq 18 years of age with a history of structural heart disease (post-MI, dilated cardiomyopathy, sarcoid myopathy, hypertrophic cardiomyopathy, etc.), who are planned for ICD implantation for: i. Secondary prevention (e.g.: VT/VF arrest, sustained VT, syncope/inducible VT) ii. Primary prevention + inducible MMVT during induction via ICD lead testing. iii. Primary prevention + fragmented QRS complex on 12-lead ECG. In addition, eligible patients will have accessible renal vasculature (determined by renal angiography).
Study Group:	In addition to ICD implantation, the subjects in this group will undergo catheter-based renal sympathetic denervation.
Control Group:	Subjects in the control group will undergo standard ICD implantation alone (if not already present).
Primary Endpoint:	Time to first event requiring any ICD therapy (appropriate or inappropriate) or Incessant VT (VT occurring below the ICD rate cut-off); this will be assessed in the on-treatment patient cohort.
Secondary Endpoints:	
 1. Appropriate ICD therapy assessed in the full intention-to-treat patient cohort 2. Inappropriate ICD therapy 3. Number of Hospitalizations for Cardiovascular Causes. 4. Total VT burden (Number of episodes). 5. All-Cause Mortality. 6. The occurrence of ICD storm, defined as \geq3 appropriate shock therapies within 24 hours. 7. Differences in BUN/creatinine measurements. 8. Procedure related adverse events including, but not limited to hematomas, pseudoaneurysms and renal artery stenosis. 9. Development of orthostatic hypotension 10. 30-day Major Complication Rate defined as death, stroke, MI or any other serious adverse events related to the treatment or procedure within the first 30 days or through hospital discharge (whichever is longer);
Primary Analytical Analysis:	Intent to treat analysis
Secondary Analytical Analysis:	Per protocol analysis

Principal Investigator: [name].
Icahn School of Medicine at Mount Sinai
[name]
[name], USA

Site, Monitoring, and Data Management Center Electrophysiology Clinical Research Group
Icahn School of Medicine at Mount Sinai
[name]
[name], USA

Data Safety and Monitoring Board: Chair: [name] (general cardiologist)
[name] (electrophysiologist)
[name] (general cardiologist)
[name] (nephrologist)
[name] (biostatistician)

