The following primary endpoint will be assessed: Time to first event requiring any ICD therapy (appropriate or inappropriate) or Incessant VT (VT occurring below the ICD rate cut-off); this will be assessed in the on-treatment patient cohort. An event requiring ICD therapy is defined as an anti-tachycardia pacing (ATP) or shock therapy. The null hypothesis of principal interest is that there will be no difference between the two treatment arms in the time to first event requiring any ICD therapy (appropriate or inappropriate) or Incessant VT in patients randomized to ICD implantation with a single renal sympathetic denervation procedure compared to patients randomized to ICD implantation alone.

5.2 SECONDARY ENDPOINTS:

The following secondary endpoints will be assessed:

1. Appropriate ICD therapy assessed in the full intention-to-treat patient cohort
2. Inappropriate ICD therapy
3. Number of Hospitalizations for Cardiovascular Causes.
4. Total VT burden (Number of episodes).
5. All-Cause Mortality.
6. The occurrence of ICD storm, defined as ≥ 3 appropriate shock therapies within 24 hours.
7. Differences in BUN/creatinine measurements.
8. Procedure related adverse events including, but not limited to hematomas, pseudoaneurysms and renal artery stenosis.
9. Development of orthostatic hypotension
10. 30-day Major Complication Rate defined as death, stroke, MI or any other serious adverse events related to the treatment or procedure within the first 30 days or through hospital discharge (whichever is longer)

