10.7 INTERIM MONITORING GUIDELINES

The objectives of interim monitoring are to (1) monitor for safety, (2) track participant accrual rates, and (3) monitor the primary and secondary outcomes for early evidence of efficacy, harm or futility. To accomplish this, summaries of data quality, accrual, adherence, distribution of baseline factors, toxicity, study endpoints and other analyses as requested will be prepared for review by the Data Safety Monitoring Committee (DSMB).

The primary outcome of the trial, rate of first event requiring any ICD therapy, is the basis for formal interim analysis plan that follows. One interim analysis and one final analysis are planned for this trial, for a total of 2 analyses. These analyses will be performed when 0.5 and 1.0 fraction of the total number of events will have been observed. Since this study will have a target number of events of 70, we will have approximately 35 events observed between each analysis time.

We will use an alpha-spending O'Brien-Fleming sequential procedure as a guideline for decision making. At the interim analysis the value of the test statistic will be compared with the alpha spending function critical values. The two alpha values will be set at 0.0054 at the interim analysis and 0.0492 at the final analysis, which equate to critical values of 2.782 and 1.967 respectively. This monitoring plan maintains the overall type I error at 0.05, given one interim analysis.

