10.8 STATISTICAL ANALYSIS

The primary analysis will be an intent-to-treat analysis that will include all randomized participants regardless of treatment actually received or follow-up schedule.

Point Estimation and Interval Estimation: We will report maximum likelihood estimates for point estimation. For routine reporting, two-sided 95% confidence intervals for all parameters will be prepared.

Disposition of Participants and Baseline Comparisons: Summaries of all participants randomized and the number who complete visits at 30-days, and every 6 months after the day of randomization will be provided for each treatment group. The treatment groups will be compared at baseline with respect to demographics, baseline measurements related to efficacy and baseline measurements related to safety.

Univariate Analysis: All outcome measures will be described in a univariate analysis. For continuous variables means and standard deviations will be calculated. For discrete and dichotomous variables we will use contingency tables.

Analysis of Primary Endpoint: The primary endpoint of this study is defined time to first event requiring any ICD therapy (appropriate or inappropriate) or Incessant VT (VT occurring below the ICD rate cut-off); this will be assessed in the on-treatment patient cohort. An event requiring ICD therapy is defined as an anti-tachycardia pacing (ATP) or shock therapy. Time to event will be estimated using Kaplan-Meier curves. Survival time will be defined as the time (in months) between randomization and the occurrence of first ICD therapy. To compare the ICD+ RSDN arm with the ICD alone arm we will use a stratified log-rank statistic (using the stratification variables from the randomization procedure). A Cox proportional hazards model with treatment and other important prognostic factors as covariates will be used for the multivariate analysis of the times to first ICD therapy. Risk ratios and their 95% confidence intervals will be computed. Patients will be included in the analysis as censored if they are alive and free of ICD events at the end of the 18-month follow-up period. Although we do not anticipate interactions between treatment and stratification factors, formal tests for interactions will be assessed using proportional hazards models. A formal test of proportional hazards will assess the significance of

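### The primary endpoint is assigned both to an undefined on-treatment cohort and to intention-to-treat, so the population for the confirmatory test is not settled

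*Combined protocol and SAP*

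**What the plan says.** Statements that put the primary endpoint in the on-treatment cohort (four places, same wording, "this will be assessed in the on-treatment patient cohort"):

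- Protocol Summary, Primary Endpoint row
- Section 5.1
- Section 10.3
- Section 10.8, Analysis of Primary Endpoint

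Statements that make the primary analysis intention-to-treat (two places):

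- Protocol Summary, Primary Analytical Analysis row: "Intent to treat analysis"
- Section 10.8, opening sentence: "The primary analysis will be an intent-to-treat analysis that will include all randomized participants regardless of treatment actually received or follow-up schedule"

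Related text:

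- The null hypothesis in 5.1 and 10.3 concerns the endpoint "in patients randomized to ICD implantation with a single renal sympathetic denervation procedure compared to patients randomized to ICD implantation alone".
- The first secondary endpoint, in the summary, 5.2 and 10.5, reads "Appropriate ICD therapy assessed in the full intention-to-treat patient cohort".
- The summary's Secondary Analytical Analysis row reads "Per protocol analysis", with no definition and no stated relation to the on-treatment cohort.
- The test itself is given in the on-treatment paragraph of 10.8: "To compare the ICD+ RSDN arm with the ICD alone arm we will use a stratified log-rank statistic". That paragraph ends with the 0.0492 level.
- Section 10.7 says "Since this study will have a target number of events of 70, we will have approximately 35 events observed between each analysis time", and names no population.

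**The concern.** The population for the primary hypothesis test must have one reading before any outcome comparison is made. Here it has at least two, and one of them is undefined. An on-treatment cohort is selected after randomisation and so loses the protection that randomisation gives.

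The direction of any bias cannot be stated in advance. Only the RSDN arm has the denervation procedure, so exclusions may fall more on that arm. Controls may also leave an on-treatment set. The summary allows ICD implantation in controls after randomisation, although 9.1.1 says they receive no further intervention. Either arm may also use the Class I or III drugs restricted by 9.1.2 and 9.2.2. Whether any of this would affect membership is unknown, because no membership rule exists. It is also unknown whether untreated patients would be dropped, censored or moved to the other group.

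A choice left open until results are visible can be made on those results. The timing of the interim look depends on the same unsettled choice, because the events that trigger it are counted in an unnamed population.

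**Working it through.** **1. Reading the passages together.** The on-treatment wording and the intention-to-treat wording both stand inside the Protocol Summary and both stand inside section 10.8. A rule that the summary or the SAP section prevails would therefore not resolve the conflict. The null hypothesis, which compares patients by randomised arm, favours intention-to-treat. Marking only the first secondary endpoint as full intention-to-treat points the other way, since it implies a different set for the primary. The available text contains no definition of on-treatment or per protocol, and no population statement in 10.7.

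**2. What an exclusion analysis could do when there is no effect.** From the plan: 19% event rate (10.6), 70 events, final critical value 1.967 (10.7). Assumed, because the documents give no figure: a fraction *f* of an arm is affected and has *k* times the risk of the rest.

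- Rate among retained patients: r = 0.19 / ((1 − f) + f·k)
- HR = ln(1 − r_RSDN) / ln(1 − r_control)
- Chance of a false finding of benefit = Φ(−1.967 − (√70 / 2)·ln HR), with √70 / 2 = 4.183

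At HR 1 this gives Φ(−1.967) = 2.5%. Worked example with 5% of RSDN excluded at twice the risk: r = 0.19/1.05 = 0.1810; HR = ln(0.8190)/ln(0.81) = 0.947; Φ(−1.967 + 4.183 × 0.0542) = 4.1%.

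| RSDN excluded | Control excluded | HR | False benefit |
|---|---|---|---|
| 2%, k = 1.5 | none | 0.989 | 2.7% |
| 2%, k = 2 | none | 0.978 | 3.0% |
| 5%, k = 2 | none | 0.947 | 4.1% |
| 5%, k = 2 | 3%, k = 2 | 0.979 | 3.0% |
| 5%, k = 2 | 5%, k = 2 | 1.000 | 2.5% |
| 3%, k = 2 | 5%, k = 2 | 1.022 | 2.0% |
| none | 5%, k = 2 | 1.056 | 1.4% |

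**3. If untreated RSDN patients are instead moved to control.** The control rate becomes (0.19 + f·k·r)/(1 + f), and √70 / 2 becomes √(70·a(1 − a)) with a = (1 − f)/2.

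| Moved from RSDN | HR | False benefit |
|---|---|---|
| 2%, k = 1.5 | 0.979 | 3.0% |
| 2%, k = 2 | 0.958 | 3.7% |
| 5%, k = 2 | 0.904 | 6.1% |
| 5%, k = 0.5 | 1.056 | 1.4% |

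**4. Simulation check.** 20,000 trials per scenario, 231 per arm, exponential times, censoring at 18 months, unstratified log-rank, final look only. Excluding 5% of RSDN at k = 2 gave 4.2%; moving them to control gave 6.5%; intention-to-treat stayed at 2.3–2.5%. These runs produce more than 70 events (462 × 0.19 = 88 before exclusions), so they do not match the formula exactly. At the larger counts the formula itself gives about 4.3% and 6.8%.

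**5. If either population could be claimed.** Testing both at 0.0492 and accepting either gives a two-sided error, at the final look alone, of 1 − P(|Z₁| < 1.967, |Z₂| < 1.967). This is about 0.058 for an assumed correlation of 0.98 and about 0.077 for 0.80.

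**The case against.** The best defence is that intention-to-treat already governs. Section 10.8 opens with it, and the summary ranks it as primary with per protocol as secondary. Other details agree. Survival time runs from randomisation. Censoring in the primary analysis is described only for consent withdrawal and for event-free patients at 18 months, with none at a treatment deviation. The sample size allows for 5% withdrawal of consent and nothing for on-treatment exclusions. All of this stands, and it makes intention-to-treat the better reading. It does not settle the matter, because the paragraph that specifies the test says otherwise and the same wording recurs in three more places.

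A second defence is that the two populations may hardly differ. RSDN is a single procedure, and under 9.1.3 patients are randomised only after angiography shows suitable renal arteries, so there is little room for non-treatment. This also stands, and it makes the smaller fractions in the tables more plausible. The documents give no rate that would confirm it.

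Third, the illustrative error rates rest entirely on assumed fractions and risks, and fall on both sides of 2.5%. That is correct, and no weight is put on any single row.

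**Conclusion.** The concern holds, and the text must be corrected before any comparison of outcomes by arm. As written, the plan contradicts itself on who is in the primary test: four statements against two, no definition of the on-treatment cohort, and no population named for the interim test or the event counts. This follows from the text alone and needs no assumption. The numerical consequence is uncertain in size and direction. In the scenarios shown it runs from 1.4% to 6.1% against 2.5%, and with the low non-treatment that 9.1.3 suggests (2% of RSDN, at 1.5 to 2 times the risk) it is 2.7% to 3.7%.

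**What to change.** 1. In the summary, 5.1, 10.3 and the endpoint paragraph of 10.8, replace the on-treatment wording with: assessed in all randomised patients as randomised (intention-to-treat).
2. In 10.7 and 10.8, state that this population governs the 0.0054 interim test, the 0.0492 final test and the counts of 35 and 70 events.
3. In the summary, 5.2 and 10.5, remove the contrast on the first secondary endpoint by stating once that all efficacy endpoints use the intention-to-treat population.
4. Use one name for the on-treatment or per-protocol cohort. Give membership rules for both arms, including whether untreated patients are excluded, censored or reassigned. Fix membership without knowledge of outcome, report exclusions by arm and reason, and label the analysis supportive.

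Steps 1 and 2 remove the contradiction; steps 3 and 4 prevent its return. The cost is wording in seven places, the per-protocol row of the summary, one sentence each in 10.7 and 10.8, and one definition.

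The statistical cost is dilution if some RSDN patients go untreated. Assume a fraction u is untreated at control risk, so the RSDN rate is (1 − u) × 0.114 + u × 0.19. Power is Φ((√70 / 2)·|ln HR| − 1.967) at the planned 70 events:

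| Untreated | HR | Power at 70 events |
|---|---|---|
| 0% | 0.574 | 64% |
| 2% | 0.583 | 62% |
| 5% | 0.595 | 58% |
| 10% | 0.615 | 53% |

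The 64% starting point, against the plan's 85%, is a separate sample-size question. At the 118 events that give 85% by this formula, the same dilution gives 83%, 80% and 75%.

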the interaction between the indicator for treatment group and log (t) in a Cox proportional hazards regression model that also includes the main effect for the randomization group. The final analysis will be based on a two tailed 0.0492 level test.

Analysis of Secondary End-points: All continuous variables will be analyzed using mixed effects models (Bagiella et al. 2000; Diggle et al. 1994; Laird and Ware 1982). Log-transformations will be used, if necessary to normalize the variables or stabilize the variance. For binary and discrete outcomes we will use generalized estimating equations (GEE) (Liang and Zeger 1986; Miller et al. 1993; Zeger and Liang 1986) to fit logistic or log-linear models that account for the dependency of the repeated measures.

Missing Data: For participants who withdraw consent to participate we will use all the information available up to the time of withdrawal. For the purpose of the primary analysis these patients will be censored at the time of withdrawal if they have not experienced the primary event. For all other variables, if the data are missing at random (MAR), that is, the probability of being missing depends only on observed values (Little and Rubin 1987), then likelihood-based methods such as mixed-effects models will be used for analysis without bias. If the fraction of missing data is small we expect that even non-ignorability can have only little effect on the final estimates. If the extent of missingness is large compared to the effect size, we will use the multiple imputation procedure proposed by Rubin (1997) and Little (1996).

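### Section 10.8 has no estimation rule for a stop at the interim for efficacy, where the ordinary hazard ratio would overstate the benefit and its 95% interval would under-cover

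*Combined protocol and SAP*

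**What the plan says.** All references are to the combined protocol and SAP.

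- **Estimation (section 10.8).** The general rule is "We will report maximum likelihood estimates for point estimation. For routine reporting, two-sided 95% confidence intervals for all parameters will be prepared". For the Cox model of the primary endpoint it adds: "Risk ratios and their 95% confidence intervals will be computed".
- **Looks (section 10.7).** "One interim analysis and one final analysis are planned for this trial, for a total of 2 analyses", at half and all of the events: "Since this study will have a target number of events of 70, we will have approximately 35 events observed between each analysis time". Early evidence of efficacy is among the stated aims of monitoring.
- **Boundary (section 10.7).** "We will use an alpha-spending O'Brien-Fleming sequential procedure as a guideline for decision making", and "The two alpha values will be set at 0.0054 at the interim analysis and 0.0492 at the final analysis". The critical values are given as 2.782 and 1.967, with overall type I error stated as 0.05.
- **Final test (section 10.8).** "The final analysis will be based on a two tailed 0.0492 level test".

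No section gives a different estimate, interval or confidence level for a result that comes from an interim stop.

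**The concern.** The sequential design governs the test but not the estimate. A trial that stops at the interim does so because its estimate was extreme, so an unadjusted HR reported after such a stop is biased towards benefit. A fixed-sample 95% interval around it makes no allowance for that selection. The boundary was set high because evidence from 35 events is thin, yet a result exactly on it would be published with an interval well clear of 1.

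At stake is the headline effect size of RSDN if the trial ends early. The reject-or-not decision is not affected. If the method is chosen only after an early stop, the choice will look data-driven.

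**Working it through.** **Inputs.** Looks at 35 and 70 events and critical values 2.782 and 1.967 (section 10.7); 18-month event rates 19% and 11.4% (section 10.6); 1:1 allocation (section 10.1). Assumptions not in the documents: proportional hazards with exponential event times, the usual information of d/4 for log HR at d events, and a boundary that is followed.

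**1. The plan's own figures.** Two-sided p for 2.782 is 0.0054 and for 1.967 is 0.0492, so these agree. Overall type I error is 1 − P(|Z1| < 2.782, |Z2| < 1.967) with correlation √0.5 = 0.707. This gives 0.0513, not the stated 0.05. With 0.0054 used at the interim, the final level would need to be 0.0479.

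**2. Design HR.** ln(1 − 0.114)/ln(1 − 0.19) = −0.1210/−0.2107 = 0.574. If the 40% reduction is read as a hazard reduction, HR is 0.60.

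**3. Result exactly on the interim boundary.**
- Estimate: exp(−2 × 2.782/√35) = 0.390.
- Ordinary 95% interval: exp(−2 × (2.782 ± 1.960)/√35) = 0.201 to 0.757.
- Repeated confidence interval: exp(−2 × (2.782 ± 2.782)/√35) = 0.152 to 1.000.

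**4. Given an efficacy stop, true HR 0.574.** Let m = −ln(0.574) × √35/2 = 1.640.
- P(stop) = 1 − Φ(2.782 − 1.640) = 12.7%.
- Mean Z given a stop = m + φ(1.142)/0.1267 = 3.280, so the geometric mean reported HR = exp(−2 × 3.280/√35) = 0.33.
- The ordinary interval misses when Z exceeds m + 1.960, with probability 0.025. Coverage given a stop = 1 − 0.025/0.1267 = 80.3%.
- The repeated interval misses when Z exceeds m + 2.782, with probability 0.0027. Coverage given a stop = 1 − 0.0027/0.1267 = 97.9%.

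The same steps at other true HRs, with coverage over both looks by numerical integration:

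| True HR | P(stop) | Mean HR given stop | Ordinary coverage given stop | Repeated coverage given stop | Ordinary coverage, both looks |
|---|---|---|---|---|---|
| 0.40 | 47.2% | 0.30 | 94.7% | 99.4% | 95.0% |
| 0.50 | 23.2% | 0.32 | 89.2% | 98.8% | 94.7% |
| 0.574 | 12.7% | 0.33 | 80.3% | 97.9% | 94.4% |
| 0.60 | 10.2% | 0.33 | 75.5% | 97.4% | 94.2% |
| 0.70 | 4.2% | 0.34 | 40.6% | 93.6% | 93.6% |

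Over both looks the lowest value between HR 0.40 and 1.0 is about 93.4%, near HR 0.75; at HR 1.0 it is 94.8%.

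**5. Final look.** The 95% interval excludes 1 without rejection only for Z between 1.960 and 1.967, that is, an observed HR from exp(−2 × 1.967/√70) = 0.6249 to exp(−2 × 1.960/√70) = 0.6259. The probability is about 0.05% to 0.3% for true HRs from 0.40 to 1.0.

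**6. Sensitivity to the event target.** The 70 events do not reproduce for 85% power, which is a separate issue. Schoenfeld's formula at HR 0.574 gives 4 × (1.967 + 1.036)²/(ln 0.574)², about 118. With an interim at 59 events, P(stop) is 25.7%, the mean reported HR 0.41 and ordinary coverage given a stop 90.3%: the same direction, but smaller.

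**The case against.** The strongest reply is that a 95% interval does not promise coverage conditional on a rare event. At HR 0.574 the chance of stopping and missing the truth is 2.5%, the nominal one-sided tail; the 80% figure is that 2.5% set against a 12.7% chance of stopping. Coverage over both looks is near nominal, and the average reported HR over both looks is 0.554 against 0.574. This stands, and it limits the weight of the point. It does not remove it, because a reader of an early-stopped trial sees only the stopped result.

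Three stronger readings are tempting, and the documents do not support them.

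- *The interval and the final test will give conflicting verdicts.* At 70 events this has probability 0.3% or less. Section 10.8 also tests with a stratified log-rank statistic but estimates from a covariate-adjusted Cox model, so the two can differ for that reason whatever the multiplier.
- *The interim multiplier must be 42% larger (2.782/1.960 = 1.42).* That is one choice of method. An interval by stagewise ordering is also valid for a group-sequential design, and at the first look it equals the ordinary one, 0.201 to 0.757.
- *The plan commits to unadjusted estimates at every look.* This is inferred from silence. The general interval sentence concerns routine reporting and does not bar supplementary estimates. Section 10.7 calls the boundary a guideline, and section 9.3.3 leaves recommendations to the DSMB, so the stopping probabilities hold only if the boundary is followed.

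**Conclusion.** The point holds as a gap confined to an efficacy stop at the interim, and it is minor. At the planned effect (HR 0.574 to 0.60) that stop has probability of about 10% to 13%. It would report an HR near 0.33 on average, with ordinary interval coverage of about 75% to 80% given the stop. The problem is worse if the true effect is weaker (41% coverage at HR 0.70, though stopping is then rarer, at 4.2%) and nearly absent if the true HR is about 0.40.

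The primary test and the sample size are not affected by this point, and the ordinary interval is adequate over the trial as a whole. The figures rest on the assumptions listed with the inputs and on an interim at 35 events; a larger event target would shrink them.

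**What to change.** Add to section 10.8: if the trial stops at the interim for efficacy, the primary hazard ratio will be reported with (a) a named, pre-specified bias-adjusted estimate, for example the bias-corrected maximum likelihood estimate for the two-look design, and (b) a repeated confidence interval, log HR ± the interim critical value × its standard error. Both stand beside the ordinary estimate and 95% interval. Item (a) is needed because the repeated interval is still centred on the unadjusted estimate. Other parameters keep ordinary 95% intervals.

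Reconcile the boundary in section 10.7 first, since 2.782 and 1.967 give an overall alpha of about 0.051 and the repeated interval takes its multiplier from there.

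The cost is a sentence or two in the SAP and a standard calculation on data already collected. The downside is a wider supplementary interval that is conservative at the planned effect (about 98% coverage given a stop at HR 0.574).
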